#### 5.6.1. Simpson-Augus Scale

The Simpson-Angus scale is a 10-item rating scale that is widely used for assessment of neuroleptic-induced Parkinsonism. It consists of 1 item measuring gait, 6 items measuring rigidity, and 3 items measuring glabella tap, tremor and salivation, respectively.

#### 5.6.2. Barnes Akathisia Scale

The Barnes Akathisia scale is a rating scale for drug-induced akathisia and includes components for rating the observable, restless movements characteristic of akathisia, the awareness of restlessness, and any distress associated with the condition.

#### 5.6.3. Abnormal Involuntary Movement Scale (AIMS)

The AIMS test is a rating scale used to measure tardive dyskinesia. There are 12 items that rate involuntary movements of various areas of the subject's body.

SPN-810

## 5.7. Columbia Suicide Severity Rating Scales (C-SSRS)

Suicidal ideation: A "yes" answer at any time during treatment to any one of the five suicidal ideation questions on the C-SSRS.

Suicidal behavior: A "yes" answer at any time during treatment to any one of the five suicidal behavior questions on the C-SSRS.

Suicidal ideation or behavior: A "yes" answer at any time during treatment to any one of the ten suicidal ideation and behavior questions on the C-SSRS.

The number and percentage of subjects will be presented at each visit by the optimized dose group and overall for suicidal ideation, suicidal behavior, and suicidal ideation or behavior.

The data listing will be provided.

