5.5 Special Safety Assessments

The following special scales will be administered in the clinic at visits designated in the Schedule of Visits and Procedures ([Table 1](#)).

5.5.1 **Simpson-Angus Scale**

The Simpson-Angus scale is a 10-item rating scale that is widely used for assessment of neuroleptic-induced Parkinsonism (Simpson 1970). It consists of 1 item measuring gait, 6 items measuring rigidity, and three items measuring glabella tap, tremor and salivation, respectively. This assessment will be administered at each visit.

5.5.2 **Barnes Akathisia Scale**

The Barnes Akathisia scale is a rating scale for drug-induced akathisia and includes components for rating the observable, restless movements characteristic of akathisia, the awareness of restlessness, and any distress associated with the condition (Barnes, 1989). This assessment will be administered at each visit.

5.5.3 **Abnormal Involuntary Movement Scale (AIMS)**

The AIMS test is a rating scale used to measure tardive dyskinesia (Munetz, 1988). There are 12 items that rate involuntary movements of various areas of the subject's body. This assessment will be administered at each visit.

5.5.4 **Columbia Suicide Severity Rating Scale (C-SSRS)**

The C-SSRS is a questionnaire that prospectively assesses suicidal ideation and behavior using a semi-structured interview to probe patient responses (Posner, 2011). The C-SSRS versions applicable to the current study are the Baseline version and the Since Last Visit version.

The Baseline version of the scale assesses lifetime suicidal ideation and behavior. This version is suitable as part of a subject's first interview and will be used at Visit 1 to identify volunteers who must not participate in the trial due to their suicidal tendencies.

The Since Last Visit version of the scale assesses any suicidal thoughts or behaviors the subjects may have had since the last administration of the C-SSRS. This version will be used for the other study visits.

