6.8.7 C-SSRS

C-SSRS outcomes will be summarized using number and percent of subjects by categories for suicidal ideation only, suicidal behavior only and suicidality (ideation and behavior combined). The summary will be presented by group of the optimized doses (<18 mg/day; 18-24 mg/day, 24-36mg/day or 36-54 mg/day) the subject received.

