# 3. GENERAL CONSIDERATIONS FOR DATA ANALYSES AND HANDLING

#### 3.1. General Statistical Methods

All statistical analysis will be performed using SAS version 9.4 or higher.

All data summaries will be presented by the optimized dose group (<18 mg/day; 18-<24 mg/day, 24-<36 mg/day or 36-54 mg/day) and overall. The optimized dose is defined as the first maintenance dose (at visit 5) for subjects entering maintenance period; otherwise using the end of study (EOS) dose for subjects discontinued prior to maintenance period.

Continuous variables will be summarized descriptively using number of subjects (n), mean, standard deviation (SD), median, minimum, and maximum.

Categorical variables will be summarized descriptively using counts and percentages. However, the number of patients with missing data will be excluded from the denominator for the percentage calculation. When the denominator for the percentage is different from the number of subjects in the treatment column header, the denominator will be clearly specified in the table or in a footnote for the table.

Individual subject data will be listed by subject ID. Unscheduled measurements (unless defined as baseline) will be excluded from summary tables but will be included in data listings. For assessments that are repeated or unscheduled, unless otherwise specified, the non-missing values from the first assessment will be used for generating summary statistics.

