#### 3.4. Visit Windows

Data from scheduled visits will be analyzed. Visits will be analyzed as scheduled. Unscheduled measurements will be excluded from the descriptive statistics and statistical analyses but will be included in listings.

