#### 5.4.2. Clinically Notable ECG

The clinically notable QT interval corrected for Fridericia's method (QTcF) are presented in appendix **9.2**. The number and percentage of subjects with potentially post-baseline Clinically Notable Value(CNV) will be summarized by optimized dose group and overall. The denominator includes all subjects with non-CNV baseline and at least one post-baseline assessment (including unscheduled visit) and the numerator is the number of subjects with non-CNV baseline and CNV at post-baseline.

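### SAP 5.7 defines the C-SSRS outcomes over the whole treatment period but tabulates them only by visit, without unscheduled assessments

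*SAP*

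**What the plan says.** SAP section 1 lists the C-SSRS among the endpoints of the primary safety objective. SAP 5.7 defines three outcomes per subject. Ideation is a yes "answer at any time during treatment to any one of the five suicidal ideation questions on the C-SSRS"; behavior, and ideation or behavior, are defined in the same way. The output is then given as "The number and percentage of subjects will be presented at each visit by the optimized dose group and overall", plus a listing. Overall here is the all-doses column described in SAP 3.1, not a row across visits.

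Two general rules deal with unscheduled data. SAP 3.1 says: "Unscheduled measurements (unless defined as baseline) will be excluded from summary tables but will be included in data listings". SAP 3.4 says: "Unscheduled measurements will be excluded from the descriptive statistics and statistical analyses but will be included in listings". For QTcF, SAP 5.4.2 sets the rule aside by counting subjects with "at least one post-baseline assessment (including unscheduled visit"). Section 5.7 has no such wording.

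Protocol 6.8.7 plans the number and percent of subjects by dose group for "suicidal ideation only, suicidal behavior only and suicidality (ideation and behavior combined"). It does not mention visits. SAP section 8 declares one change from the protocol, to the compliance calculation.

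On the instrument, Protocol 5.5.4 states: "The Baseline version of the scale assesses lifetime suicidal ideation and behavior". It assigns that version to Visit 1 and the Since Last Visit version to all other visits. Footnote a of Protocol Table 1 says that the Visit 1 C-SSRS is the end-of-study assessment of the preceding double-blind study.

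**The concern.** The definition and the table answer different questions. A definition that spans treatment yields one number per dose group: how many subjects were ever positive. A by-visit table yields up to 24 post-baseline columns, each with its own attendees, and none of them is that number. For a rare but serious outcome in subjects aged 6 to 17, the ever-positive proportion is what a safety reader looks for first.

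Two further features weaken the table. A positive found between scheduled visits is left out of it. The Visit 1 column may also rest on a different recall period from the columns beside it, and the SAP neither separates Visit 1 nor mentions versions.

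**Working it through.** The plan states no C-SSRS figure, so there is none to reproduce. The check compares the texts and adds one bound.

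**1. Can the incidence be recovered from the by-visit table?** Post-baseline visits run from Visit 2 to Visit 25 (Protocol Table 1), so there are 25 − 2 + 1 = 24. Let n_j be the number of subjects positive at visit j, N the number of subjects, and E the number ever positive at a scheduled visit. Then

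max(n_j) ≤ E ≤ min(N, Σ n_j).

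The lower limit applies when every positive comes from subjects already counted at the visit with the highest count. The upper limit applies when no subject is positive twice. Two illustrations, with counts chosen only to show the width and full attendance assumed:

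- One positive at each of Visits 2 to 6 (6 − 2 + 1 = 5 visits): E lies between 1 and 5.
- One positive at each of Visits 2 to 25 (24 visits): E lies between 1 and 24.

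The same table is compatible with a 24-fold range over full follow-up. If some subjects are positive only at unscheduled assessments, the on-treatment total can also exceed Σ n_j.

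**2. What happens to a positive found at an unscheduled assessment?**

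- Protocol 4.2 allows unscheduled visits at the Investigator's discretion in all study periods.
- SAP 3.1 and 3.4 send such data to listings only.
- The Since Last Visit version looks back only as far as the previous C-SSRS (Protocol 5.5.4). An event recorded at an unscheduled C-SSRS therefore need not reappear at the next scheduled one.
- Protocol 5.1.2.1 says that an increased C-SSRS score becomes an AE only if it meets AE criteria.

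Taken together, a positive found only at an unscheduled assessment and not judged an AE would appear in the listing and nowhere else.

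**3. Is Visit 1 comparable with later visits?** Protocol 5.5.4 gives Visit 1 the lifetime version. Table 1 footnote a makes it the preceding study's final assessment, and the documents do not state which version was used there. On the first text the recall period differs from later visits; on the second it is unknown. SAP 5.7 adds a further ambiguity: its definitions are confined to treatment, while its table covers every visit, so it is unclear whether Visit 1 belongs.

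**4. Is the change from the protocol declared?** Protocol 6.8.7 gives number and percent by category and dose group and does not split by visit. SAP 5.7 splits by visit and specifies nothing across visits. Section 8 does not mention it.

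**The case against.** The strongest reply is that nothing is lost. The C-SSRS listing holds every assessment, including unscheduled ones. Protocol 6.8.7 still stands and could be programmed alongside the SAP table. If each affected subject is positive only once, the scheduled counts add up to the number ever positive. All of this is true, but a listing is not a summary, SAP 5.7 does not call for the protocol's table, and the counts add up only when there are no repeat positives.

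One could also read each visit column as cumulative to that visit. The SAP does not say so and gives no denominator for it. SAP 3.1 has a sentence taking the first non-missing value for repeated or unscheduled assessments, but this does not bring a later unscheduled positive into the table.

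Three stronger readings are tempting, and the documents do not support them:

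- **That the table will show a fall after Visit 1 caused purely by the recall period.** The version at Visit 1 is unsettled. Exclusion criterion 5 (Protocol 4.1.2) bars subjects with suicidality confirmed at the last visit of the preceding study, which depletes positives at Visit 1 to an unknown extent. The series could fall, stay flat or rise.
- **That events found at unscheduled visits reach no table.** Events meeting AE criteria are counted in the TEAE tables of SAP 5.1, including those for serious events and for withdrawals, whenever they are found. The loss is also conditional: Table 1 has no unscheduled column, and no passage requires a C-SSRS at such a visit.
- **That a suicidality rate can be quoted to size the problem.** The documents contain none.

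**Conclusion.** The point holds in this form: SAP 5.7 does not tabulate the outcomes that it defines, it leaves out unscheduled assessments without the exception given to QTcF, and it departs, undeclared, from the natural reading of Protocol 6.8.7. This part rests on the text and needs no assumption about rates.

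The size is a bound. With 24 post-baseline visits and repeat positives possible, by-visit counts can be compatible with up to a 24-fold range in the number of subjects ever positive. That extreme assumes full attendance and equal counts at every visit; the actual range depends on how often the same subjects are positive again.

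The Visit 1 part is weaker. Comparability is not shown, and Protocol 5.5.4 and Table 1 footnote a must be reconciled, but no direction of distortion can be claimed. The AE tables narrow the gap without closing it. This is a reporting defect in a primary safety endpoint that should be corrected; it does not undermine the data.

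**What to change.** In SAP 5.7:

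1. Make the main table the number and percentage of subjects with any post-baseline positive answer, scheduled or unscheduled, for ideation, for behavior, and for either, by optimized dose group and overall. Use subjects with at least one post-baseline C-SSRS as the denominator. State the exception to SAP 3.1 and 3.4, as 5.4.2 does for QTcF.
2. Reconcile Protocol 5.5.4 with Table 1 footnote a, then show Visit 1 separately, labelled with the version actually used.
3. Keep the by-visit table as supportive.
4. List any remaining departure from Protocol 6.8.7 in SAP section 8.

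A comparison against a since-last-visit result from the preceding studies is not proposed, because these documents do not show that one exists.

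The cost is one additional table from data already collected, a separate display of Visit 1, and a few sentences in the SAP.

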## 6. EFFICACY ANALYSES

Absolute value and CFB (if applicable) of efficacy endpoints will be analyzed descriptively at each scheduled visit by the optimized dose group and overall using the Safety Population, unless otherwise specified.

# 6.1. Retrospective-Modified Overt Aggression Scale (R-MOAS)

The Retrospective-Modified Overt Aggression Scale (R-MOAS) was developed to gauge the severity of aggressive behavior. Parents rate the frequency over the past week of 16 aggressive behaviors in four areas: verbal aggression (VE); physical aggression toward others (PH); aggression toward oneself (PR); and destruction or hostile misuse of property (SE).

VE, PH, PR, SE subdomain scores and total score will be collected on eCRF and no derivation is needed.

# 6.2. Clinical Global Impression - Severity (CGI-S)

The CGI-S is evaluated on a 7-point scale, where 1 = Normal, not at all ill, asymptomatic, 2 = Borderline III, 3 = Mildly III, 4 = Moderately III, 5 = Markedly III, 6 = Severely III, and 7 = Extremely III.

# 6.3. Clinical Global Impression - Improvement (CGI-I)

The CGI-I is evaluated on a 7-point scale where 1 = Very much improved, 2 = Much improved, 3 = Minimally improved, 4 = No change, 5 = Minimally worse, 6 = Much worse, and 7 = Very much worse. The CGI-I results will be summarized using the absolute value (i.e., no CFB).

There are caregiver and investigator CGI-I assessments.

#### 7. EXPLORATORY ANALYSES

Absolute value and CFB (if applicable) of quality of life continuous variables will be analyzed descriptively at each scheduled visit by the optimized dose group and overall, unless otherwise specified. The quality of life categorical variables will be analyzed using count and percentage at each scheduled visit by the optimized dose group and overall, unless otherwise specified.

# 7.1. The Child Health Questionnaire Parent Form 28-item (CHQ-PF28)

The recorded score on CRF needs to be transformed in 0-100 range before calculating subscales and summary scores.

Item	Recorded Score on CRF	Final Raw Score	Transformed Score
1.1;	1	5	((Final Raw Score -1)/4) * 100
5.2;	2	4.4	
9.4	3	3.4	
	4	2.2	
	5	1	
2.1a-2.1c;	1	1	((Final Raw Score -1)/3) * 100
3.1;	2	2	
3.2;	3	3	
9.2a-9.2b	4	4	
4.1	1	6	((Final Raw Score -1)/5) * 100
	2	5	
	3	4	
	4	3	
	5	2	
	6	1	
5.1a-5.1c;	1	1	((Final Raw Score -1)/4) * 100
6.1a-6.1c;	2	2	
8.1a-8.1c;	3	3	
9.3a-9.3b	4	4	
	5	5	
7.1a-7.1c;	1	5	((Final Raw Score -1)/4) * 100
8.2;	2	4	
9.1a-9.1b	3	3	1
	4	2	]
	5	1	]

The physical functioning summary score (PHS) and psychosocial health summary score (PSS) are calculated in three steps.

SPN-810

• Step1: z-score standardizations.

Subscale	Sum of	Formulas for z-score standardizations
	Transformed	
	Score	
Physical Functioning (PF)	2.1a-2.1c	PF_Z=(PF - 90.8525408) / 16.3826344
Role/Social Limitations -	3.2	RP_Z=(RP - 91.4951246) / 18.9079749
Physical (RP)		
General Health Perceptions	8.1a-8.1c,1.1	GH_Z=(GH - 66.6958379) / 19.3564297
(GH)		
Bodily Pain/Discomfort (BP)	4.1	BP_Z=(BP - 78.6833515) / 20.7355708
Role/Social Limitations -	3.1	REB_Z=(REB - 90.4013015) / 19.5067502
Emotional/Behavior (REB)		
Parental Impact - Time (PT)	9.2a-9.2b	PT_Z=(PT - 83.8816188) / 20.2901603
Parental Impact - Emotional	9.1a-9.1b	PE_Z=(PE - 73.9788476) / 21.406013
(PE)		
Self-Esteem (SE)	7.1a-7.1c	SE_Z=(SE - 79.2555314) / 17.8308361
Mental Health (MH)	6.1a-6.1c	MH_Z=(MH - 77.2595806) / 13.6861999
Behavior (BE)	5.1a-5.1c,5.2	BE_Z=(BE - 72.3086051) / 17.1447913
Family Activities (FA)	9.3a-9.3b	NA
Global Health (GGH)	1.1	NA
Global Behavior (GBE)	5.2	NA
Family Cohesion (FC)	9.4	NA
Change in Health (CH)	8.2	NA

• Step 2. PHS raw and PSS raw scores

PHS\_raw = (PF\_Z \* .37138) + (RP\_Z \* .34493) + (BP\_Z \* .27883) + (GH\_Z \* .29460) + (REB\_Z \*-.01178) + (PT\_Z \* .09113) + (PE\_Z \* .06063) + (SE\_Z \* -.09480) + (MH\_Z \* - .08263) + (BE\_Z \* -.12675)

PSS\_raw = (PF\_Z \* -.09243) + (RP\_Z \* -.06973) + (BP\_Z \* -.05514) + (GH\_Z \* -.05547) + (REB\_Z\* .21155) + (PT\_Z \* .16944) + (PE\_Z \* .19823) + (SE\_Z \* .24792) + (MH\_Z \* .25335) + (BE\_Z \* .27911)

• Step 3. Transformation of PHS raw and PSS-raw

PHS = 50 + (PHS raw \* 10)

PSS = 50 + (PSS raw \* 10)

*Note: More details can be found in the Child Health Questionnaire (CHQ) Scoring and Interpretation Manual (HealthActCHQ).* 

Subscales, PHS and PSS will be analyzed descriptively by the optimized dose group and overall and by visit.

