5.3.3 Stress Index for Parents of Adolescents (SIPA)

The Stress Index for Parents of Adolescents (SIPA) is a screening and diagnostic instrument that identifies areas of stress in parent–adolescent interactions, allowing examination of the relationship of parenting stress to adolescent characteristics, parent characteristics, the quality of the adolescent–parent interactions, and stressful life circumstances in parents of adolescents (11-19 years old). The SIPA consists of 90 items divided in three major domains, the Adolescents Domain (AD), the Parent Domain (PD) and the Adolescent-Parent Relationship Domain (APRD), which include the following subscales: moodiness/emotional lability, social isolation/withdrawal, delinquency/antisocial, failure to achieve and persevere, relationship with spouse/partner, social alienation and incompetence/guilt. The SIPA includes 22-item Life Stressors (LS) Scale and the Index of Total Parenting Stress (TS).

Parents respond to the first 90 items using a 5-point rating scale ranging from *Strongly Disagree* (5) to *Strongly Agree* (1) and the final 22 items by indicating *Yes* (Y) or *No* (N).

The SIPA will be administered to caregivers of adolescents (13-17 years of age) at each visit after the first 6 months (Visits 5 to 25). For subjects who discontinue early, this will be administered at the EOS (Visit 25).

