#### 7.3. Stress Index for Parents of Adolescents (SIPA)

The SIPA is for 13-17 years of age only.

The SIPA includes 112 items. The first 90 items are divided in three major domains and 8 subscales showing in the table below. They use a 5-point rating scale ranging from Strongly Disagree (5) to Strongly Agree (1): 1=SD (Strongly Disagree), 2=DA (Disagree), 3=NS (Not Sure), 4=A (Agree), and 5=SA (Strongly Agree).

Note: Items 2, 3, 4, 5, 9, 10, 15, 25, 28, 34, 40, 45, 49, 54, 66, 69, 74, 81, 83, 85, 87, and 88 are rated from Strongly Disagree (5) to Strongly Agree (1). To be consistent with other items, they have to be reversed  $(1 \rightarrow 5, 2 \rightarrow 4, 3 \rightarrow 3, 4 \rightarrow 2, and 5 \rightarrow 1)$  prior to calculating subscales and domains.

Domain	Subscale	Sum of Items
Adolescent	Moodiness/Emotional Lability (MEL)	10 items (1, 6, 11, 16, 21, 26, 31, 36, 41, 46)
Domain	Social Isolation/ Withdrawal (ISO)	10 items (2, 7, 12, 17, 22, 27, 32, 37, 42, 47)
(AD)	Delinquency/Antisocial (DEL)	10 items (3, 8, 13, 18, 23, 28, 33, 38, 43, 48)
	Failure to Achieve or Persevere (ACH)	10 items (4, 9, 14, 19, 24, 29, 34, 39, 44, 49)
Parent	Life Restrictions (LFR)	10 items (51, 52, 55, 56, 59, 63, 67, 71, 75, 79)
Domain (PD)	Relationship with Spouse/Partner (REL)	9 items (60, 64, 68, 72, 73, 76, 77, 80, 81)
	Social Alienation (SOC)	7 items (53, 54, 57, 58, 61, 65, 69);
	Incompetence/Guilt (INC)	8 items (62, 66, 70, 74, 78, 82, 86, 90)
Adolescent-		16 items (5, 10, 15, 20, 25, 30, 35, 40, 45, 50,
Parent		83, 84, 85, 87, 88, and 89)
Relationship		
Domain		
(APRD)		

SPN-810

- AD = MEL + ISO + DEL + ACH
- PD = LFR + REL + SOC + INC
- Total Parenting Stress (TPS) = AD + PD + APRD

The Life Stressors (LS) Scale includes the last 22 items (Items 91-112) with responses of 1=Yes and 0=No.

• Life Stressors (LS) = Sum last 22 items (Items 91-112)

TPS, each domain, each subscale, and LS scale will be analyzed descriptively by the optimized dose group and overall and by visit.

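### SAP 7.1 sums CHQ-PF28 items but standardises them with constants that fit only item means, so PHS and PSS are mis-scored as written; SAP 7.3 gives contradictory SIPA coding

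*SAP*

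**What the plan says.** **CHQ-PF28 (SAP 7.1).** The section opens with the item transformation: "The recorded score on CRF needs to be transformed in 0-100 range before calculating subscales and summary scores". The Step 1 table then lists the items in each subscale under a header that calls for the sum of the transformed scores. In the extracted text this header runs into its neighbour as "Sum of Formulas for z-score standardizations", and its remaining words fall on the next line. No division by the number of items is given. Each subscale is then standardised, for example "PF_Z=(PF - 90.8525408) / 16.3826344" for the three-item Physical Functioning scale and "BE_Z=(BE - 72.3086051) / 17.1447913" for the four-item Behavior scale. Step 2 weights the z-scores, and Step 3 sets each summary score to 50 plus 10 times the weighted total. A note refers to the scoring manual for further detail. On reporting: "Subscales, PHS and PSS will be analyzed descriptively by the optimized dose group and overall and by visit".

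**SIPA (SAP 7.3 and Protocol 5.3.3).** The SAP describes the first 90 items as "ranging from Strongly Disagree (5) to Strongly Agree (1): 1=SD (Strongly Disagree", and continues that key up to 5 for Strongly Agree. It then lists 22 items that "are rated from Strongly Disagree (5) to Strongly Agree (1). To be consistent with other items, they have to be reversed". The protocol has one direction for all 90 items: "Parents respond to the first 90 items using a 5-point rating scale ranging from *Strongly Disagree* (5) to *Strongly Agree* (1").

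**The concern.** A z-score needs its value and its reference mean on the same scale. Here the value is a sum that can reach 200, 300 or 400, while the reference means all lie between 66.7 and 91.5. If the rule is followed, PHS and PSS lose their centre of 50. The error is not a constant that cancels in change scores, because the inflation is two-, three- or fourfold depending on the subscale and absent for single items. The reported multi-item subscales are also stretched by the same factors, including the two-item Family Activities scale, though their order is kept.

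For the SIPA, a reversal rule works only if the stored coding is known. If the rule is applied to the wrong coding, the stress score is partly or wholly inverted.

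Protocol 1.5 says changes in these instruments will be used to evaluate improvement in quality of life, and SAP Table 1 lists change from baseline in them as endpoints.

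**Working it through.** The plan gives no worked score to reproduce, so the test is internal: with Step 3 in the form 50 + 10 × weighted z, a child at the reference means must score 50.

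**Inputs.** All come from the SAP 7.1 table and Step 2. n is the number of items, m and s are the printed constants, and w is the Step 2 weight. If every item averages m, the sum is n·m, so the z-score under the written rule is (n − 1)·m/s. Under item means it is 0.

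| Subscale | n | m | s | m/n | z with sums | w (PHS) | w (PSS) |
|---|---|---|---|---|---|---|---|
| PF | 3 | 90.85 | 16.38 | 30.3 | 11.09 | .37138 | −.09243 |
| GH | 4 | 66.70 | 19.36 | 16.7 | 10.34 | .29460 | −.05547 |
| PT | 2 | 83.88 | 20.29 | 41.9 | 4.13 | .09113 | .16944 |
| PE | 2 | 73.98 | 21.41 | 37.0 | 3.46 | .06063 | .19823 |
| SE | 3 | 79.26 | 17.83 | 26.4 | 8.89 | −.09480 | .24792 |
| MH | 3 | 77.26 | 13.69 | 25.8 | 11.29 | −.08263 | .25335 |
| BE | 4 | 72.31 | 17.14 | 18.1 | 12.65 | −.12675 | .27911 |
| RP | 1 | 91.50 | 18.91 | 91.5 | 0 | .34493 | −.06973 |
| BP | 1 | 78.68 | 20.74 | 78.7 | 0 | .27883 | −.05514 |
| REB | 1 | 90.40 | 19.51 | 90.4 | 0 | −.01178 | .21155 |

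**Which scale the constants belong to.** RP, BP and REB are single items, so their constants must be on 0-100. The multi-item constants are of the same size. If they referred to sums, the reference child would average 30.3 per item on PF, 18.1 on BE and 16.7 on GH (column m/n), against 78.7 to 91.5 on the single items. That is not credible.

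**Child at the printed means, sum rule** (10·w·z, in the order PF, GH, PT, PE, SE, MH, BE):

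- PHS = 50 + 41.19 + 30.45 + 3.77 + 2.10 − 8.43 − 9.33 − 16.04 = 93.71
- PSS = 50 − 10.25 − 5.73 + 7.00 + 6.85 + 22.04 + 28.60 + 35.31 = 133.83 (unrounded terms)

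With means, both are 50.00.

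**Other records (PHS / PSS).**

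| Record | Means | Sums |
|---|---|---|
| All items at 100 | 58.44 / 64.05 | 111.87 / 175.45 |
| All items at 0 | 0.89 / 1.75 | 0.89 / 1.75 |
| 10-point gain on every item | +5.8 / +6.2 | +11.1 / +17.4 |

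With means, putting each subscale at 0 or 100 according to the sign of its weight gives ceilings of 77.79 (PHS) and 78.90 (PSS).

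**Change in one subscale.** Effect on PSS of a 10-point gain on each item:

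- Behavior: 40/17.1448 × 0.27911 × 10 = 6.5 with sums; 10/17.1448 × 0.27911 × 10 = 1.6 with means.
- Mental Health: 30/13.6862 × 0.25335 × 10 = 5.6 with sums; 1.9 with means.

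**Sign reversal.**

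- PSS, one Mental Health item up one category (+25) and item 3.1 down one (−33.3). The item 3.1 term is −33.3/19.5068 × 0.21155 × 10 = −3.62. Sums: 4.63 − 3.62 = +1.0. Means: 1.54 − 3.62 = −2.1.
- PHS, one Physical Functioning item up one category (+33.3) and item 3.2 down one (−33.3). Sums: 7.56 − 6.08 = +1.5. Means: 2.52 − 6.08 = −3.6.

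**SIPA.** The item lists cover items 1 to 90 once each (40 AD + 34 PD + 16 APRD). Of these, 22 are listed for reversal: 7 AD, 5 PD and 10 APRD. Take a parent who answers Strongly Agree to the 68 other items and Strongly Disagree to the 22, and apply the listed reversal (6 − code):

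| Stored coding | Total | APRD | Opposite answers, total |
|---|---|---|---|
| All items 1=SD to 5=SA | 68×5 + 22×5 = 450 | 80 | 90 |
| Only the 22 stored SD=5 to SA=1 | 68×5 + 22×1 = 362 | 40 | 68×1 + 22×5 = 178 |
| All items SD=5 to SA=1 (protocol) | 68×1 + 22×1 = 90 | 16 | 450 |

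**The case against.** The strongest reply is that nothing shows how the scores are programmed. The SAP refers to the CHQ scoring manual, which is not available here, and a programmer who knows it may average the items. A PSS of 134 to 175 on a scale centred at 50 would also be conspicuous in output review. That limits the claim to scoring as written. It does not rescue the text: a pointer to further detail does not override an explicit column header, and SAP 7.2 and 7.3 use summation literally for their own scales. If means are in fact used, the SAP misdescribes the analysis.

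The sign reversals are constructed single-child examples. Their frequency cannot be derived, and the SAP plans group summaries, not classification of individuals. The baseline for CHQ change is also unclear: the schedule first collects CHQ at Visit 5, and SAP Table 2 defines an efficacy baseline only for R-MOAS and CGI-S. These points stand, so the examples show that relative weights are distorted, not how often a conclusion would change. Levels are wrong in any case.

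On the SIPA, the three readings are not equally supported. The full five-value key and the stated aim of matching the other items favour 1 for Strongly Disagree. That is fair, but the range phrase in the same sentence and the protocol say the opposite, so the stored coding needs checking. Calling a total maximum or minimum stress assumes that a higher score means more stress, which neither section states.

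**Conclusion.** The point holds, as something that should be fixed. As written, SAP 7.1 shifts a child at the reference means by +43.7 on PHS and +83.8 on PSS, multiplies each multi-item subscale's contribution to change by 2 to 4, and stretches those subscales by the same factor. Single-item subscale scores and all-zero records are unaffected. That item means were intended is inferred from the size of the constants, the single-item scales and the 50 + 10z form, all within the SAP. The SIPA text is contradictory, and identical answers can total anything from full score to minimum depending on the stored coding; this concerns ages 13 to 17 only. Both defects are confined to exploratory, descriptive quality-of-life outputs.

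**What to change.** **SAP 7.1.** Change the Step 1 column header from the sum to the mean of the transformed scores for all multi-item subscales, including Family Activities; single items need no change. State at the same time what happens when an item is missing, because the any-item-missing rule in SAP 3.6 names only efficacy variables.

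**SAP 7.3.** First confirm the stored response codes against the eCRF. Then state that one coding and the one reversal it requires so that all items point the same way, remove the conflicting anchors, and state the direction of the score. Correcting the wording without this check could itself invert the score.

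**Test records.** Score one CHQ record at the printed means (expected 50 and 50), entered at item level: entered as subscale values it returns 50 under either rule and would miss the error. Real items are discrete, so also use a record with every item at 100 (expected 58.4 and 64.0). For the SIPA, score one maximum-stress and one minimum-stress record.

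**Cost.** One header correction and a sentence on missing items for the CHQ; one eCRF code check and a rewritten paragraph for the SIPA. Data collection is unchanged.
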